9. STUDY ENDPOINTS

9.1. The primary outcomes:

- **Efficacy endpoint**

- 1- Change in WHO Ordinal Scale for clinical improvement (baseline to end of study will be measured on days 1,7,14 and 28).

The World Health Organization (WHO-WHO) has proposed the “Ordinal Scale of Clinical Evaluation of the World Health Organization” presented below as a means of generating a numerical value to assess the health status of the participant to allow comparisons to be made in clinical studies. The scale is shown in the table below and will be used to assess a secondary effectiveness target in this study.

Patient State	Descriptor	Score
Uninfected	Uninfected; no clinical evidence and viral RNA detected	0
Ambulatory	Symptomatic; independent	1
	Symptomatic; assistance needed	2
Hospitalized: Moderate diseases	Hospitalized, no oxygen therapy	3
	Hospitalized; oxygen by mask or nasal prongs	4

	MGC Pharma Clinical Study Protocol	Protocol No.: MGC-009
		Version 02, 05 Sep 2021
		Page 34 of 76
A Phase IIb, double blind, placebo-controlled clinical study designed to evaluate the effect of CimetrA in patients diagnosed with COVID-19		CONFIDENTIAL

Hospitalized: Severe diseases	Hospitalized; oxygen by NIV or high flow	5
	Hospitalized; mechanical ventilation	6
	Mechanical ventilation and vasopressors, dialysis or ECMO	7
Dead	Dead	8

2- Change in COVID-19-Related Symptoms score (measured on days 1,7, 14, 28)

• **Safety Endpoints**

Safety will be assessed through collection and analysis of adverse events, blood and urine laboratory assessments and vital signs.

9.2. **The secondary outcomes:**

- Number of participants with depending on oxygen supplementation through day 28 since onset of symptoms
- Change in inflammatory marker levels - IL-6, IL-1 β , IL-12, TNF α , IFN- γ , CRP, NLR (Neutrophil / Lymphocyte ratio) (days 1, 2, 4, 7) compared to baseline
- Pharmacokinetic profile of the study drug on day 1 through 24 Hrs.
- Incidence and duration of mechanical ventilation
- Incidence of Intensive Care Unit (ICU) stay during COVID-19 complication
- Percentage of participants with definite or probable drug related adverse events
- Long term adverse events of COVID-19 on Day 28
- The Impact covid_19 on quality of life of patients on Days 1, 14 and 28

9.3. **The exploratory outcomes:**

- Course of change in D Dimer levels compared to baseline

	MGC Pharma Clinical Study Protocol	Protocol No.: MGC-009
		Version 02, 05 Sep 2021
		Page 35 of 76

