10. STUDY DESIGN AND PROCEDURES

240 adult patients who suffer from COVID-19 infection and do not participate in any other clinical trial. Patient must not agree to participate in any new clinical study during the study duration. Study will take place during patient's hospitalization due to COVID-19 infection. The study will last up to 4 weeks, until conclusion on day 28. In case of hospital discharge within the study period, follow up will continue per protocol until day 28 wherever the subject will be located, depending on the status of the patient and study schedule.

If patient discharged, visits will be performed via phone call, if he still hospitalized, visits will be performed at corona department.

Only on day 28, all the patients must undergo clinic visit, they will arrive to the research clinic (only patient who will be under quarantine will have a phone call visit).

The study is not designed to include participants from a special population, so that patients with mental and intellectual problems, lack of judgment, children under the age of 18 and pregnant women will not be allowed to participate, or any patient who have a legal guardian.

Standard of care treatment acceptable to be used while patient participates in study:

Treatment will include:

Supportive care - symptomatic

Painkillers

Anticoagulant therapy

	MGC Pharma Clinical Study Protocol	Protocol No.: MGC-009
		Version 02, 05 Sep 2021
		Page 36 of 76
A Phase IIb, double blind, placebo-controlled clinical study designed to evaluate the effect of CimetrA in patients diagnosed with COVID-19		CONFIDENTIAL

Steroids

REMDESIVIR - Compassionate treatment

Antibiotic treatment as needed

Inhalations if necessary

Oxygen

The treatments offered above are given according to the guidelines of the Ministry of Health.

The treatment will be given to the patient according to the clinical judgment of the medical staff and in accordance with the patient's health condition, and therefore the treatment does not have to be the same in each of the medical centers participating in the study.

10.1. **Enrollment**

Each candidate subject will be reviewed for an inclusion/exclusion criteria. After signing the ICF, the candidate subject will be asked to provide a medical history and undergo a physical examination, including measurement of blood pressure, pulse, temperature (PO), body weight and height, saturation, respiratory rate, vas scale, news score.

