13. **CONCOMITANT MEDICATIONS DURING THE STUDY**

13.1. **General guidelines**

All prior treatments received by the subject within 60 days of the initial screening visit will be recorded on the subject's CRF including the treatment's name, indication and the start and stop dates.

All concomitant medications taken by the subject (including prescription, over-the-counter, herbal supplements and health store products) must be recorded on the CRF, along with the indication and start and stop dates as well as daily dose.

13.2. **Allowed Concomitant Medications/Therapies during Study**

Concomitant medications allowed to be used in this study are those used at screening to control existing medical condition and/or those taken during the study to treat possible adverse events. All concomitant medications used to treat adverse events will be recorded in the subject's medical file and on the appropriate CRF page.

If intake of a drug should become necessary for any reason during the course of the study, the subject is required to inform the Investigator immediately, who will record the drug, the dose and the time of administration in the subject's CRF.

Standard of care treatment acceptable to be used while patient participates in study :

Treatment will include:

Supportive care - symptomatic

Painkillers

Anticoagulant therapy

Steroids

	MGC Pharma Clinical Study Protocol	Protocol No.: MGC-009
		Version 02, 05 Sep 2021
		Page 54 of 76
A Phase IIb, double blind, placebo-controlled clinical study designed to evaluate the effect of CimetrA in patients diagnosed with COVID-19		CONFIDENTIAL

REMEDSIVIR - Compassionate treatment

Antibiotic treatment as needed

Inhalations if necessary

Oxygen

The treatments offered above are given according to the guidelines of the Ministry of Health.

The treatment will be given to the patient according to the clinical judgment of the medical staff and in accordance with the patient's health condition, and therefore the treatment does not have to be the same in each of the medical centers participating in the study.

13.3. **Potential Adverse Events and risks for the patient in the study**

During Phase II study on 50 COVID-19 patients no drug related adverse events were reported. The full safety profile is presented above .

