A Phase IIb, double blind, placebo-controlled clinical study designed to evaluate the effect of CimetrA in patients diagnosed with COVID-19		CONFIDENTIAL

The 3 groups will be compared with the ANOVA test or Kruskal Wallis non-parametric test, following by post-hoc analysis for pairs differences.

Additional Efficacy Parameters of Interest

A count and percentage of participants responding to each of the exploratory efficacy endpoints will be presented. The groups will be compared with a chi-squared test or a Fisher’s exact test.

Safety Analysis

The primary safety variable, the cumulative incidence (and 95% CI) of device related adverse events (AEs) throughout the study, will be presented in tabular format and will include incidence tables by severity.

Serious adverse events, device-related SAEs, adverse events (by type and overall), device-related AE, adverse device reactions and device malfunction rates will be compared between the study arms with a Fisher’s exact test.

Serious adverse events will be listed and discussed individually.

PK test

Actual times of dosing and blood collection at various time points will be recorded in source documents as well as CRF’s. Objectives of PK sampling are to measure values of CimetrA active ingredients in plasma at different time point after first administration of study medications and at different time point after multiple administrations during steady state.

PK samples will be processed and frozen on site. Labels have been prepared for the site again containing patient No., visit No., type of test (PK) and time point. Upon completion of the study, samples will be sent to selected analytical laboratory with dedicated courier service. The PK parameters will be obtained from plasma concentration data for curcumin and boswellia.

	MGC Pharma Clinical Study Protocol	Protocol No.: MGC-009
		Version 02, 05 Sep 2021
		Page 65 of 76
A Phase IIb, double blind, placebo-controlled clinical study designed to evaluate the effect of Cimetra in patients diagnosed with COVID-19		CONFIDENTIAL

Analyses of PK data will be based on the PK Set, which will include all subjects who received at least one treatment and for whom concentration data is available.

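### The inflammatory-marker comparison is fixed as an unadjusted test although the Day 1 value, centre and baseline steroid use are on hand: a modest, cheaply recovered loss of precision

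*Protocol*

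**What the plan says.** Section 9.2 lists "Change in inflammatory marker levels" as a secondary outcome: IL-6, IL-1β, IL-12, TNFα, IFN-γ, CRP and "NLR (Neutrophil / Lymphocyte ratio) (days 1, 2, 4, 7) compared to baseline".

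Section 17, Secondary Efficacy Analysis, gives one method: "The 3 groups will be compared with the ANOVA test or Kruskal Wallis non-parametric test", with post-hoc pairwise comparisons afterwards. It names no baseline value, centre or background drug. The only covariate sentence in section 17 is optional and generic, and it stands under Subset Analyses, which deals with the primary endpoint.

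Sections 10 and 13.2 list steroids among the acceptable standard-of-care treatments, together with "REMDESIVIR - Compassionate treatment". They place these treatments under Ministry of Health guidelines and then add: "The treatment will be given to the patient according to the clinical judgment of the medical staff". They also state that "the treatment does not have to be the same in each of the medical centers participating in the study".

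The data for an adjustment largely exist. Table 5 schedules the cytokines and the haematology and biochemistry tests on Day 1. Section 17 stratifies the randomisation by center. Section 13.1 has prior treatments from the 60 days before screening entered on the CRF, and concomitant medications "must be recorded on the CRF, along with the indication and start and stop dates as well as daily dose".

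**The concern.** Cytokine control is the product's stated rationale, so the markers are the trial's test of mechanism. Steroids are anti-inflammatory. A patient already on them when the Day 1 sample is drawn may start from a lower value than an untreated patient, and the same change from baseline may then mean different things in the two. This is general pharmacology; the protocol does not state it.

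An unadjusted comparison leaves that variation in the error term. It also leaves out the Day 1 marker value, and it leaves out centre, although centre is the randomisation stratum and background care may differ by centre. At stake is the precision of a secondary, mechanistic result, and how easily a reader could put an observed difference down to arms that happened to differ in baseline steroid use.

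**Working it through.** **The plan's own figure.** Section 17 gives f = 0.20, α = 0.05, three arms of 80 and power of at least 80%, for the WHO scale only. With noncentrality N·f² = 240 × 0.04 = 9.6 and 2 and 237 degrees of freedom, the noncentral F gives 79.3%; reaching 80% takes 246 patients (82 per arm). The figure reproduces to within one point. The protocol gives no power for the markers.

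**Assumptions.** f = 0.20 is borrowed for a marker, measured on the SD among patients with the same steroid status. p is the share on steroids at the Day 1 sample, and d is the steroid effect on marker change in the same SD units. The documents give neither. All 80 patients per arm are taken to contribute a sample.

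**Gain from the steroid term.** Omitting it multiplies the error variance by 1 + p(1−p)d² and divides the noncentrality by the same factor.

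| p | d | Variance factor | Noncentrality | Power, unadjusted |
|---|---|---|---|---|
| 10% | 0.3 | 1.008 | 9.52 | 79.0% |
| 30% or 70% | 0.5 | 1.05 | 9.12 | 77.1% |
| 50% | 0.5 | 1.06 | 9.04 | 76.7% |
| 50% | 0.8 | 1.16 | 8.28 | 72.7% |
| 50% | 1.0 | 1.25 | 7.68 | 69.3% |

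With the term included, power stays at about 79%. The loss is therefore 79.3 − 79.0 = 0.3 points in the first row and 79.3 − 69.3 = 10.0 points in the last, where the factor 1.25 equals 25% more patients.

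**Type I error.** In 20,000 simulated null trials per scenario (the last four rows, with p = 30% in the first of them), the unadjusted test rejected in 4.9% to 5.1%. It is valid on average.

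**Chance imbalance.** The SD of the difference in steroid use between two arms is √(2p(1−p)/80): 7.2 percentage points at p = 30% and 7.9 at p = 50%. A gap of 15 points or more between some pair of arms arises in 12% and 16% of trials respectively. Within those trials the unadjusted false-positive rate is about 6–7% at d = 0.5, 8% at d = 0.8 and 10% at d = 1.0, against 4–5% with adjustment. Steroid use was drawn independently of centre here; stratification would reduce the gaps to the extent that use differs by centre.

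**One loss, not two.** At p = 50% and d = 1.0 the imbalance moves a pairwise contrast with an SD of 0.079. Squared, that is 0.00625, and 0.00625 / (2/80) = 0.00625 / 0.025 = 25%. This is the same 25% as in the table.

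**Gain from the Day 1 value.** With equal variances σ² and baseline-to-follow-up correlation r, a change score has variance 2σ²(1−r) and ANCOVA leaves σ²(1−r²). The ratio is (1+r)/2. For assumed r = 0.3 to 0.7 it is 0.65 to 0.85, so the variance is 35% to 15% lower. This gain and the steroid gain may overlap, since steroid use can already show in the Day 1 value, and they should not simply be multiplied.

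**The case against.** The strongest reply is that nothing is invalid and that covariates for secondary endpoints usually belong in the SAP. The first part stands. The second does not quite: the protocol names a test for these outcomes, and one of its two options, Kruskal-Wallis, takes no covariate. The covariate sentence under Subset Analyses could be stretched to the markers, but it is optional and stands with the primary endpoint.

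It is also fair that the size rests on assumptions with no documentary floor. Eligible patients have SpO₂ of at least 94% on room air and no signs of severe pneumonia, so low baseline steroid use is plausible, and then the steroid term gains almost nothing. Study success depends on the WHO scale alone.

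A reader might infer more than the documents support:

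- Bias or an inflated overall error rate. Randomisation prevents both; only trials with a large chance gap show a raised rate.
- Noise and chance imbalance as separate harms. They are the same variance.
- Remdesivir as an equal case. It is listed only as compassionate treatment, and any effect on the markers would be indirect.
- Days 2 to 7 as the peak of steroid effects. The protocol gives no such timing.
- A cure for patients who start steroids after the Day 1 sample and randomisation. A baseline flag does not capture them, and adjusting for later starts would condition on a post-randomisation event.
- Wholly discretionary care. The protocol places it under Ministry of Health guidelines before it invokes clinical judgment.

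**Conclusion.** The point holds as a modest matter of precision. Section 17 fixes an unadjusted test for marker outcomes whose main predictors are scheduled or recorded. No figure in the protocol is wrong because of it.

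The steroid term is worth between 0.3 and about 10 power points (1% to 25% more patients) over the assumed range of 10% use with a 0.3 SD effect to 50% use with a 1.0 SD effect. The Day 1 value is likely to matter at least as much if its correlation with follow-up is moderate. The change is worth making because it is cheap and because an adjustment added after unblinding would look data-driven.

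**What to change.** In section 17, Secondary Efficacy Analysis, give the markers their own sentence: an ANCOVA of each log-transformed marker at Days 2, 4 and 7, adjusted for the log Day 1 value, centre (small centres pooled by a prespecified rule) and steroid use (yes/no) at the time of the Day 1 sample. Name a rank-based ANCOVA as the non-parametric alternative in place of Kruskal-Wallis. With the log Day 1 value in the model, the treatment contrast is the same for the log value and for its change, so the endpoint is still a change from baseline, on a ratio scale. Leave remdesivir out of the main model or keep it for a sensitivity analysis.

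Do not adjust for drugs started after randomisation; tabulate those starts by arm. How these patients are handled must be reconciled with section 11.3(b). That rule terminates a subject who begins a dose increase of an existing medication and keeps such subjects out of the primary analyses, while sections 10 and 13.2 allow steroids by clinical judgment. The protocol should say what becomes of these patients' marker samples.

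Cost: a few lines of analysis text and a Day 1 steroid start time on the CRF. Section 13.1 asks only for dates, although section 13.2 already asks for the time of administration when a drug becomes necessary during the study. No sample or visit is added.

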The overall significance level for this study is 5% using two-tailed tests, except for treatment by center/region interaction that will be tested at a significance level of 10%.

When multiple comparisons between the groups are made, the chance of finding a significant difference in one of the comparisons is greater than the stated significance level, therefore we will use pot-hoc analysis.

Efficacy endpoints:

Time to sustained clinical improvement (as defined earlier).

Safety Endpoints

The safety endpoints of adverse events and tolerability will be assessed by review of all safety parameters, including adverse events.

	MGC Pharma Clinical Study Protocol	Protocol No.: MGC-009
		Version 02, 05 Sep 2021
		Page 63 of 76
A Phase IIb, double blind, placebo-controlled clinical study designed to evaluate the effect of CimetrA in patients diagnosed with COVID-19		CONFIDENTIAL

The incidence of adverse events will be assessed as a function of severity and association to the device. The time of resolution of the adverse events and need for treatment will also be analyzed.

Analysis Sets

The ITT analysis set will serve as the main set for safety assessments.

The primary and secondary performance efficacy assessments will also be performed on the PP and the ITT analysis sets.

Statistical Analysis

Demographic and Baseline

Demographic and baseline condition related characteristics will be tabulated and compared between the study arms by data type. Continuous variables will be summarized by a mean, standard deviation, minimum, median and maximum and categorical variables by a count and percentage.

Primary Efficacy Analysis

The primary efficacy endpoint of the study is the mean change in the WHO Ordinal Scale. It will be evaluated using a General Linear Model ANOVA test.

Subset Analyses

The primary endpoint will also be evaluated stratified by center using a General Linear Model ANOVA test.

A sensitivity analysis of the primary endpoint will be performed to assess the impact of missing data on the study outcome.

Adjustment for other covariates such as demographics or other baseline participant characteristics may be performed by adding these variables into a multivariate linear regression.

Secondary Efficacy Analysis

	MGC Pharma Clinical Study Protocol	Protocol No.: MGC-009
		Version 02, 05 Sep 2021
		Page 64 of 76

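### Three yes/no secondary outcomes are assigned ANOVA or Kruskal-Wallis with unnamed post-hoc pairs, while chi-squared and Fisher's tests are attached to exploratory outcomes that include continuous D-dimer change

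*Protocol*

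**What the plan says.** Under Secondary Efficacy Analysis in section 17 the protocol gives one sentence: "The 3 groups will be compared with the ANOVA test or Kruskal Wallis non-parametric test, following by post-hoc analysis for pairs differences". No other test is named there.

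The secondary list in section 9.2 includes "Number of participants with depending on oxygen supplementation through day 28 since onset of symptoms" and "Incidence of Intensive Care Unit (ICU) stay during COVID-19 complication", together with the incidence and duration of mechanical ventilation. The duration is not binary. Oxygen dependence, ventilation incidence and ICU incidence are yes/no for each patient.

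Tests for proportions appear elsewhere in the section. Under Additional Efficacy Parameters of Interest: "A count and percentage of participants responding to each of the exploratory efficacy endpoints will be presented". This continues: "The groups will be compared with a chi-squared test", with Fisher's exact test as the alternative. Section 9.3 lists two exploratory outcomes, the course of D-dimer change and the occurrence of secondary infections. Under Safety Analysis: "device-related AE, adverse device reactions and device malfunction rates will be compared between the study arms with a Fisher’s exact test".

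On error control: "The overall significance level for this study is 5% using two-tailed tests". The protocol notes that several comparisons raise the chance of a significant result, and concludes: "therefore we will use pot-hoc analysis". It does not name the procedure.

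**The concern.** The methods do not match the data type in either direction. Yes/no secondary outcomes get methods for continuous or ranked data, and a continuous exploratory outcome gets a count, a percentage and a chi-squared test.

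ANOVA post-hoc tests, and Dunn's test after Kruskal-Wallis, use one variance pooled over all three arms. For a yes/no outcome the variance is p(1 − p), so it differs between arms whenever the risks differ. A two-dose trial has to allow for one dose working while the other does not. In that case the pooled variance is too small for the inactive dose against placebo, which then looks effective too often. It is too large for the active dose against placebo, which loses some precision. Oxygen, ventilation and ICU use are clinically weighty outcomes, and the pair comparisons are what would separate the doses.

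**Working it through.** **Inputs from the protocol.** 80 patients per arm, 240 in total, 1:1:1; two-sided 5%; three groups. No event rates are given for the yes/no outcomes, so all risks below are assumptions, scanned from 0% to 50%.

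**The plan's own figure.** The only stated power is for the primary ANOVA: f = 0.20, N = 240, at least 80%. Noncentral F with 2 and 237 degrees of freedom and noncentrality f²N = 0.04 × 240 = 9.6 gives 79.3%; 80% needs N = 246. The figure is reproduced to within a point, so 80 per arm is used below. The protocol states no operating figure for the secondary outcomes.

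**Step 1: overall test.** On 0/1 data Kruskal-Wallis equals (N − 1)/N = 239/240 times the Pearson chi-squared statistic. Exact enumeration of three binomial arms at equal risks of 2% to 50% gives an error of 3.9% to 5.0% for both the F test and Kruskal-Wallis. There is no inflation here.

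**Step 2: pair test, two arms at risk p, third arm at risk q.** The pooled variance is [2p(1 − p) + q(1 − q)]/3. The true variance for the equal pair is p(1 − p). With critical value t = 1.970 (237 df), the unadjusted large-sample error is

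2[1 − Φ(t × √(pooled/true))].

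For 20/20/5%: pooled = (0.32 + 0.0475)/3 = 0.1225; true = 0.16; root ratio = √0.7656 = 0.875; 1.970 × 0.875 = 1.724; error = 8.5%.

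Ceiling, with q = 0: root ratio = √(2/3) = 0.816; 1.970 × 0.816 = 1.609; error = 10.8%.

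Third arm higher, 10/10/20%: pooled = (0.18 + 0.16)/3 = 0.1133; true = 0.09; root ratio = 1.122; error = 2.7%.

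**Step 3: exact enumeration, n = 80 per arm, error for the equal pair.**

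| Assumed risks | SE pooled/true | Unadjusted, formula | Unadjusted, exact | Tukey | Bonferroni | Two-arm chi-squared |
|---|---|---|---|---|---|---|
| 20/20/20% | 1.000 | 4.9% | 5.0% | 1.9% | 1.7% | 5.0% |
| 40/40/20% | 0.943 | 6.3% | 6.5% | 2.8% | 2.4% | 4.7% |
| 20/20/10% | 0.924 | 6.9% | 7.1% | 3.0% | 2.7% | 5.0% |
| 10/10/5% | 0.918 | 7.1% | 7.2% | 3.1% | 2.8% | 4.9% |
| 20/20/5% | 0.875 | 8.5% | 8.7% | 4.0% | 3.7% | 5.0% |
| 10/10/0% | 0.816 | 10.8% | 10.6% | 5.2% | 5.2% | 4.9% |
| 10/10/20% | 1.122 | 2.7% | 2.7% | 0.8% | 0.7% | 4.9% |
| 5/5/20% | 1.338 | 0.8% | 0.8% | 0.1% | 0.1% | 4.2% |

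Over all scenarios run, the maximum is 5.5% for Tukey and 5.2% for Bonferroni. Requiring a significant F test first changes little: 6.4% at 20/20/10% and 8.7% at 20/20/5%. With the third arm lower, unadjusted Dunn tests give 5.9% to 10.2%, and Dunn with Bonferroni at most 4.9%.

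**Step 4: standard errors.** In moderate scenarios (third arm at a quarter to a half of the common risk) the pooled standard error is 0.875 to 0.943 of the true one for the equal pair. For the unequal pair the ratio is √(2 × pooled/[p(1 − p) + q(1 − q)]), which runs from 1.03 to 1.09. At 20/20/10% it is √(0.2733/0.25) = 1.046. The error in the standard error is therefore about 3% to 13%.

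**The case against.** The strongest reply has five parts.

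- **Coverage.** A reader might infer that every secondary outcome goes to ANOVA or Kruskal-Wallis, and that at least four yes/no outcomes are affected. The protocol does not support that. Related adverse events go to Fisher's exact test under Safety Analysis (worded as device-related), and the pharmacokinetic outcome has its own non-compartmental analysis. Three yes/no outcomes remain.
- **Size.** A reader might also infer that the false-positive rate doubles. That needs an unadjusted procedure, two equal arms and almost no events in the third. The stated reason for the post-hoc analysis is multiplicity, which suggests an adjusted procedure, and with Tukey or Bonferroni the error stays near or below 5%. Equal risks bring no per-pair inflation, and a higher third arm makes the test conservative.
- **Rank tests.** Pooling over three arms is a property of Dunn's test, not of every follow-up to Kruskal-Wallis. Pairwise Mann-Whitney uses only the two arms compared and, on 0/1 data, nearly equals the two-arm chi-squared test.
- **Intervals.** The protocol promises a 95% interval only for the safety variable, so the standard-error problem would reach a reported interval only if one is added for the secondary pairs.
- **Level of detail.** Test by outcome, and choice of post-hoc procedure, are often left to the SAP.

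The first four stand and limit the point. The last stands only in part. An unnamed post-hoc procedure alone would be no finding. Here, however, the protocol does name methods and attaches them to the wrong data types; matching by data type is stated only for the demographic and baseline comparisons. An SAP that follows the text inherits the mismatch, and one that departs from it contradicts the protocol.

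**Conclusion.** The point holds in limited form. Three yes/no secondary efficacy outcomes have no test for proportions assigned, and one continuous exploratory outcome is given one.

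The overall tests are sound on 0/1 data. The harm is confined to pair comparisons that pool the variance. If these are unadjusted, the error for two equal arms is about 6.5% to 9% when the third arm's risk is moderately lower, with a ceiling of about 10.8%. It falls below 5% when the third arm is higher. With Tukey or Bonferroni it is about 5% or less, so a general doubling of the error rate cannot be claimed. An adjusted procedure changes the critical value but not the pooled standard error, which is off by about 3% to 13% in moderate scenarios.

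These sizes rest on assumed event rates, 80 evaluable patients per arm and a post-hoc procedure that the protocol does not name. The primary analysis is unaffected. This is a correction worth making to the secondary analysis, not a threat to the trial's main conclusion.

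**What to change.** In section 17, assign tests by data type.

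- Limit ANOVA and Kruskal-Wallis to continuous or ordinal outcomes, and move D-dimer change there. Keep chi-squared or Fisher's test for secondary infections.
- For oxygen dependence, ventilation incidence and ICU incidence, compare each active arm with placebo by chi-squared or Fisher's exact test, or by Cochran-Mantel-Haenszel stratified by centre, since the Randomization paragraph stratifies by centre. Report the risk difference with a two-sample 95% interval (Newcombe or Miettinen-Nurminen).
- Name a multiplicity adjustment for the two comparisons with placebo, such as Holm or Bonferroni. This is needed: two unadjusted chi-squared tests against placebo give a family-wise error of about 9% under equal risks of 10% to 30%, which would replace one inflation with another. Bonferroni at 5%/2 = 2.5% each bounds it at 5%.
- Name the post-hoc procedure for the continuous outcomes in the same sentence.

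The cost is one paragraph. Chi-squared and Fisher's tests are already named in the section; sample size, data collection and the primary analysis do not change.
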